9.4.2 Recording Adverse Events

A "pre-existing" condition is one that is present before investigational product dosing and is reported as part of the subject's medical history. Pre-existing conditions should be reported as an adverse event only if the frequency, intensity, or character of the pre-existing condition worsens during the course of the study. Adverse events will be collected from the time the informed consent is signed to the end of the subject's participation in the study.

Subjects should be instructed to report all potential adverse events to the investigator, and, queried in a non-leading manner, without specific prompting (e.g., "How are you feeling?"). The site study staff should assess emerging symptoms of dissociative reaction similar to those caused

by NMDA antagonists including memory impairment, disturbance in time, body or environmental perception, stilted speech, emotional withdrawal, impaired coordination, motor retardation, bizarre reasoning or illusory experiences in any sensory perception, or confused state; such symptoms may be captured as adverse events.

To avoid vague, ambiguous, or colloquial expressions, all adverse events should be recorded in standard medical terminology rather than in the subject's own words. Each adverse event will also be described in terms of duration (start and stop date), severity, relationship to investigational product, action(s) taken, and outcome. Diagnoses (rather than symptoms) should be recorded wherever possible.

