10.2 Baseline (Week 0)

At Visit 2 (Baseline Visit), the following procedures and assessments will be performed:

- Medical history update
- Concomitant medication use assessed
- Rescue medication supplies returned, appropriate use assessed, and compliance/accountability performed
- Adverse events assessed
- Sitting vital signs (blood pressure and pulse after 5 minutes)
- Brief physical examination
- Electrocardiogram after 5 minutes in supine position
- Urine pregnancy test for females of childbearing potential
- Urine drug test

- Breathalyzer test for alcohol
- Urine sample for urinalysis
- Bedside Sensory Testing Kit
- Pain scores reported by subjects during the Screening Period and diary compliance evaluated by the interactive response technology system for raw score and for variability among scores by automated transmission of pain scores from the handheld devices

Subjects who continue to meet all entry criteria and are randomized by the interactive response technology system will undergo the following procedures and assessments:

- Blood samples for fasting (8 hours) serum chemistry and hematology
- HADS
- S-STS
- BPI-DPN
- SF-MPQ-2
- QOL-DN
- Insomnia Severity Index
- Investigational product dispensed
- Rescue medication dispensed

Subjects will be reminded on how to record their pain on the device

Subjects will also be reminded about appropriate expectations around their participation in a clinical study

Review of these educational materials may be repeated for some or all subjects depending on findings of an ongoing blinded data review (e.g., if pain score variability is increased on a subject or site level. On each day until returning to the study site at Week 2, subjects will record the following on the handheld device:

- At bedtime: average pain intensity, worst pain intensity, pain on walking, and use of rescue medication during the past 24 hours.
- Upon waking: DSIS

The investigative site staff will contact study subjects by telephone one week following Week 0 to reinforce the diary completion and assess adverse events.

Subjects will be instructed to return to the study site at Week 2.

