12.6.1 Adverse Events

A TEAE is defined as an adverse event with an onset that occurs after receiving investigational product, or a continuing adverse event diagnosed prior to the date of first dose of investigational product, which increases in severity after the start of dosing. Adverse events will be categorized by system organ class and preferred term with the Medical Dictionary for Regulatory Activities.

Summary tables for TEAEs will include number and percent of subjects experiencing TEAEs by system organ class and preferred term. If a subject has more than 1 TEAE that codes to the same preferred term, the subject will be counted only once for that preferred term. Similarly, if a subject has more than 1 TEAE within a system organ class category, the subject will be counted only once in that system organ class category.

The following TEAE summaries will be provided for the Screening Period and Treatment Period (including Follow-Up):

- Overall summary of TEAEs
- TEAEs by system organ class and preferred term
- Drug-related TEAEs by system organ class and preferred term
- TEAEs by system organ class, preferred term, and severity

Serious TEAEs and TEAEs leading to investigational product discontinuation will be identified.

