10.1 Adverse Events

Treatment-emergent adverse events (TEAEs) will be those occurring during or after administration of the first dose of study drug until 30 days after the final dose of study drug. Due to the nature of this study, the date and time of first dose of study drug was not collected on the CRF. Therefore, the following algorithm will be used to determine if the adverse events are treatment-emergent:

- Earliest Possible AE Start Date ≥ Baseline Visit and Study Drug Dispensation and
- Latest Possible AE Start Date ≤ 30 Days After the Final Dose of Study Drug

Adverse events that started on the Baseline Visit (Study Day 1) that are the result of abnormal clinically significant electrocardiograms (ECGs) or clinical laboratory tests collected prior to study drug dispensation will not be considered TEAEs.

The following System Organ Class (SOC) AEs for abnormal clinically significant clinical laboratory tests will be reviewed to determine if the AE is not treatment-emergent:

- Investigations
- Infections and infestations (with the Preferred Term = "Urinary tract infection")

AEs that started prior to first dosing of study drug, but become worse in severity after receiving study drug will be considered treatment-emergent. The determination of whether or not an adverse event is classified as "treatment emergent" (i.e. TEAE) is not dictated by the classification of "relationship to study drug" collected on the CRF, but rather by the temporal relationship of the adverse event to the administration of study drug.

A related study drug TEAE is defined as any TEAE with at least a possible relationship to the study drug as assessed by the investigator or that is missing the assessment of causal relationship whose relationship to the study drug could not be ruled out. Relationships of "possibly related", "probably related", or missing are collected on the CRF, then those adverse events will be considered related study drug TEAEs. If the "unrelated" or "unlikely related" are collected on the CRF, then those adverse events will be considered not related study drug TEAEs.

Severity is assigned to each adverse event collected on the CRF. Maximum severity has the following order: "life threatening", "severe", "moderate", and "mild" as possible collection options on the CRF. A missing severity will be treated as "unknown" for analysis purposes.

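### SAP 10.1 exempts only ECG and laboratory findings from TEAE status on Day 1, so other same-day events documented before dispensing are counted as treatment-emergent (minor)

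*SAP*

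**What the plan says.** SAP 10.1 starts from a principle: "Treatment-emergent adverse events (TEAEs) will be those occurring during or after administration of the first dose of study drug", up to 30 days after the final dose. It then explains that "the date and time of first dose of study drug was not collected on the CRF" and substitutes a date rule. The lower bound is "Earliest Possible AE Start Date ≥ Baseline Visit and Study Drug Dispensation and"; the upper bound is 30 days after the final dose. SAP 5.1.1 assumes that the first dose was taken on Day 1.

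One sentence takes Day 1 events out: "Adverse events that started on the Baseline Visit (Study Day 1) that are the result of abnormal clinically significant electrocardiograms (ECGs", together with those from laboratory tests collected before dispensing. A second step supports it. By organ class, "AEs for abnormal clinically significant clinical laboratory tests will be reviewed to determine if the AE is not treatment-emergent". The classes listed are Investigations and, within Infections and infestations, the single preferred term for urinary tract infection. AEs that began before the first dose and worsen afterwards are TEAEs. The section closes by making timing relative to study drug, and not the causality rating, decide TEAE status.

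The protocol's definition in 12.6.1 is: "A TEAE is defined as an adverse event with an onset that occurs after receiving investigational product". For Visit 2, Protocol 10.2 gives a first list that includes AE assessment, vital signs, brief physical examination, ECG, urine sample and the Bedside Sensory Testing Kit. It then continues: "Subjects who continue to meet all entry criteria and are randomized by the interactive response technology system will undergo the following procedures and assessments". Blood sampling and dispensing of study drug come in that second list.

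**The concern.** The exemption shows that the SAP's authors expected findings made at Visit 2 before dispensing to appear as AEs dated Day 1. It deals with two sources of such findings and leaves out the others in the same visit list. A symptom that began that morning and was reported to the AE question, or a reaction to the pin and filament testing, precedes any dose. The date rule cannot separate it from an event that began after the first capsules.

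The laboratory review has a related gap. Protocol 9.4.2 tells sites that "Diagnoses (rather than symptoms) should be recorded wherever possible", and the SAP's own urinary tract infection entry shows that a laboratory finding recorded as a diagnosis can code outside Investigations.

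At stake is the accuracy of the TEAE tables. The overall summary and the table by organ class and preferred term (14.3.1.1 and 14.3.1.2) are both marked for topline. Safety is descriptive only, so readers will compare raw counts between arms of about 75. SAP 10.1 also treats a TEAE with no causality assessment as related, so a pre-dose event could reach the related-TEAE table.

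**Working it through.** The documents state no figure on this point to reproduce. The check applies the rule to cases and then bounds the size.

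**Step 1: what the rule can see.** First-dose date and time: not collected (SAP 10.1). First-dose day: assumed to be Day 1 (SAP 5.1.1). AE timing: start and stop date, with no clock time mentioned (Protocol 9.4.2). Date comparison alone therefore cannot order two events on Day 1.

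**Step 2: the rule applied to cases.**

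| Event | Result under SAP 10.1 |
|---|---|
| ECG or laboratory finding, Day 1, before dispensing | Not a TEAE (exempt) |
| Symptom, vital sign, examination or sensory-test AE with Day 1 onset, before dispensing | TEAE |
| Onset on Day 1 after the dose | TEAE; same dates as the row above |
| Reported at Visit 2, onset Day -3 | Not a TEAE |
| Partial date whose earliest possible date is before Day 1 | Not a TEAE |
| Onset Day -3, worsens after dosing | TEAE |

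Only the second row conflicts with Protocol 12.6.1 and with the SAP's own principle. SAP 4.7 does not list the TEAE rule among its changes from the protocol.

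**Step 3: the laboratory list.** The exemption sentence has no organ-class limit. The limit is in the review list. A pre-dose glucose, haemoglobin or urine protein finding recorded as a diagnosis outside the listed classes is exempt on the text, but the planned review would not look for it.

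**Step 4: size.** Planned subjects per arm: 75 (SAP 4.3). SAP 10.1 counts a subject once at each level of summary. One affected subject with no other TEAE adds 1/75 = 1.3 percentage points to the arm's rate; a subject who already has a TEAE adds nothing to that rate.

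The share q of subjects with a non-exempt pre-dispensing AE on Day 1 is not in the documents. Assume that q is equal across arms and independent of other TEAEs, and that true TEAE rates are p = 30% and 40%. The observed rate is 1 - (1 - p)(1 - q).

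| q | Subjects per arm (75q) | Observed rates | Difference |
|---|---|---|---|
| 0.5% | 0.4 | 30.4% and 40.3% | 9.95 points |
| 1% | 0.75 | 30.7% and 40.6% | 9.9 points |
| 2% | 1.5 | 31.4% and 41.2% | 9.8 points |
| 5% | 3.75 | 33.5% and 43.0% | 9.5 points |

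For noise, compare the SD of a between-arm difference when both arms have a true rate of 30%:
- without the extra events: sqrt(2 × 0.30 × 0.70 / 75) = 7.48 points;
- with q = 2%: sqrt(2 × 0.314 × 0.686 / 75) = 7.58 points.

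The increase is about 0.1 point. Taken alone, these events have a between-arm SD of sqrt(2 × 0.02 × 0.98 / 75) = 2.3 points, but that is not the noise added to the comparison.

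**The case against.** The strongest reply is that the SAP's principle already excludes events known to precede dosing. The date rule is an acknowledged proxy, and counting a Day 1 event of unknown timing as a TEAE is the cautious choice for safety reporting. The affected set is also small:
- Events with onset before Day 1 already fail the date rule.
- Blood pressure and heart rate outside the limits in Protocol 7.2 should prevent randomization, because eligibility is verified at Visit 2.
- Protocol 9.4.1 and 9.4.2 send conditions present before dosing to medical history unless they worsen.
- Protocol 9.4.1 does not treat a laboratory abnormality as an AE unless it has symptoms, needs intervention, or leads to interruption or discontinuation of product.

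Most of this stands as a limit on size. It does not remove the conflict. AEs are collected from consent, so a new symptom on the morning of Visit 2 can be recorded as one. The SAP found it necessary to write an explicit exemption, and that exemption omits other pre-dispensing sources. Caution justifies keeping events of unclear timing, but not events documented as earlier.

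A reader might also infer that laboratory AEs outside the two listed classes become TEAEs by rule. The text does not say so: the exemption covers all laboratory tests, and only the look-up is narrow. Nor can a reader infer that every such event raises an arm's TEAE rate by 1.3 points, since each subject is counted once.

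**Conclusion.** The point holds in a limited form and is minor. An AE with Day 1 onset, documented before dispensing through a source other than ECG or laboratory testing, is classified as treatment-emergent, contrary to Protocol 12.6.1 and to the SAP's own principle. Laboratory AEs recorded as other diagnoses are exempt but could be missed.

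The consequence is a small over-count: at most 1.3 percentage points per affected subject with no other TEAE. Under the assumptions above, a 10-point difference between arms shrinks by 0.05 to 0.5 points. The calculation rests on 75 treated subjects per arm, an assumed q of 0.5% to 5%, and independence; the documents supply only the first, as a planned number.

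A reader might infer that the safety comparison is biased for or against the drug. The documents do not support that. The events precede dosing in a randomized, double-blind trial, so they are expected equally in all arms.

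**What to change.** In SAP 10.1, extend the Day 1 exemption to any AE documented as starting before study drug was dispensed, whichever procedure or question revealed it. Replace the two-class review list with a review, completed before unblinding, of all AEs with a Day 1 start date in all organ classes. State that events of unclear timing, and events that worsen after dosing, remain TEAEs. Reclassified events stay visible in Listing 16.2.7.3, which holds AEs not considered treatment-emergent.

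The cost is a change of SAP wording and a short blinded review that extends one already planned. The drawback is that few events may prove reclassifiable, because AEs are described by date and not by clock time. An ECG or laboratory AE can be tied to a dated result; a symptom dated Day 1 often cannot.

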9.4.3.2 Action Taken for Adverse Events

For each reported adverse event, an investigator must document the action taken according to the following criteria:

- No action taken
- Concomitant medication taken
- Hospitalization or prolongation of hospitalization

- Discontinued study
- Nondrug therapy
- Other (specify)

The investigator must also document the action taken in regards to investigational product (as a result of a given adverse event) according to the following criteria:

- Dose not changed
- Investigational product interrupted
- Investigational product withdrawn
- Not applicable
- Unknown

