All adverse events will be coded and summarized by System Organ Class (SOC) and Preferred Term (PT) based on Medical Dictionary for Regulatory Activities (MedDRA) version 19.0 coding dictionary. This data will be summarized in a frequency distribution. Subjects may have more than one TEAE record per SOC and PT. At each level of subject summarization, a subject will be counted once if he/she reports one or more TEAE record at that specific level. For tables summarized by SOC and PT, the events will be displayed in the order of descending frequency counts for all treatments by SOC and then PT within SOC.

The number of subjects with at least one of the following adverse events, percentages for each category by treatment, and the number of total events will be included in an overall treatment-emergent adverse events summary table:

- Any TEAEs
- Related TEAEs
- Maximum Severity TEAEs
- Serious TEAEs
- Related, Serious TEAEs
- TEAEs Leading to Study Discontinuation
- Related TEAEs Leading to Study Discontinuation
- TEAEs Leading to Death

Summaries including the number of subjects and percentages of the following adverse events by SOC and PT will be provided:

- Any TEAEs
- Related TEAEs
- Maximum Severity TEAEs

- Serious TEAEs
- TEAEs Leading to Study Discontinuation

Additionally, TEAEs will be summarized by descending frequency counts of PT for all treatments. All adverse event data collected will be provided in subject listings. Subset subject listings will also be provided by serious treatment-emergent adverse events and deaths; by treatment-emergent adverse events leading to study discontinuation; any adverse events that are not considered to be treatment-emergent; and by adverse events leading to study discontinuation that are not considered to be treatment-emergent.

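### Protocol 12.6.1 identifies TEAEs leading to product discontinuation; SAP 10.1 labels its discontinuation rows and TEAE subset listing as study discontinuation only

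*SAP*

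**What the plan says.** Protocol 12.6.1 (Adverse Events) closes with: "Serious TEAEs and TEAEs leading to investigational product discontinuation will be identified". The verb is identify; the section does not ask for a count by arm of these events.

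Protocol 9.4.3.2 (Action Taken for Adverse Events) sets two items for each event. The first is a general action, and one of its options is "Discontinued study". For the second, the section adds: "The investigator must also document the action taken in regards to investigational product (as a result of a given adverse event". The bracket closes there and a separate option list follows, which includes "Investigational product withdrawn".

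SAP 10.1 (Adverse Events) plans counts by arm: "percentages for each category by treatment, and the number of total events will be included in an overall treatment-emergent adverse events summary table". Two of the listed categories are "TEAEs Leading to Study Discontinuation" and "Related TEAEs Leading to Study Discontinuation". The first of these labels also heads one of the SOC/PT summaries, and a subset listing of TEAEs uses the same trigger (Listing 16.2.7.2 in SAP 14). The title of the SOC/PT table, 14.3.1.7 in SAP 13, says only discontinuation, without stating of what.

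SAP 10.1 also says: "All adverse event data collected will be provided in subject listings".

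SAP 4.7 (Analyses Changes from the Protocol) covers the HADS cut-offs, the efficacy population, the pooled 200 mg and 50 mg group, the site factor and the interim analysis. It does not mention adverse-event discontinuation categories, and it says the remaining protocol analyses are consistent with the SAP.

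**The concern.** The protocol and the SAP name different events. Stopping the drug because of an adverse event is a direct measure of tolerability, and tolerability of multiple dose levels is a secondary objective. Leaving the study is a later and possibly separate step. If the SAP label is programmed literally from the general action, a TEAE for which the investigator recorded product withdrawal but not study discontinuation would drop out of the by-arm rows, the SOC/PT summary and the subset listing. A reader of the topline adverse-event table would then see a tolerability count on a narrower basis than the one the protocol names, with nothing in SAP 4.7 to say so.

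**Working it through.** The plan states no figure for this point, so the check is mainly a comparison of texts.

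**Step 1. The category in each document.** Protocol 12.6.1: TEAE leading to discontinuation of the product. SAP 10.1: TEAE leading to discontinuation of the study. The public texts differ, and SAP 4.7 does not mention it.

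**Step 2. Whether the two can diverge in the data.** Protocol 9.4.3.2 collects them as separate items, so the four combinations are:

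| Product withdrawn | Discontinued study | Protocol 12.6.1 category | SAP 10.1 label, read literally |
|---|---|---|---|
| yes | yes | in | in |
| yes | no | in | out |
| no | yes | out | in |
| no | no | out | out |

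The second row is the gap. A plausible route runs through the visit window. Visit 4 is at Day 28 ± 2 (Protocol Table 3), so a subject who stops capsules for an adverse event a few days earlier could still attend it. SAP 7.1 counts subjects who completed Visit 4, so that subject could be a study completer with the product withdrawn.

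**Step 3. Which outputs carry the label.**
- Overall TEAE table, 14.3.1.1 (marked topline): 2 of 8 listed categories.
- SOC/PT summaries: 1 of 5.
- Subset listings: 1 of 4 is the TEAE discontinuation listing, 16.2.7.2.

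That gives 2 + 1 + 1 = 4 places. Listing 16.2.7.4 uses the same wording but covers events that are not treatment-emergent. Protocol 12.6.1 speaks only of TEAEs, so this listing is not counted.

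**Step 4. Size per subject.** SAP 4.3 gives about 75 subjects per arm, with three active arms.
- One arm: 1/75 = 1.33 percentage points.
- All Doses column: 3 × 75 = 225, and 1/225 = 0.44 percentage points.

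These figures assume safety-population arms of about the planned size. The documents give no basis for how many subjects would fall in the gap, so no total is calculated.

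**The case against.** The strongest reply is that the two labels are close to synonymous in this trial. Protocol Table 3, note c, sends subjects who stop randomized treatment early to the Week 4 procedures. At that visit they hand back the drug and the diary device, and only a safety visit 7 days later remains. Protocol 7.4 speaks of adverse events that warrant permanent withdrawal from the study, and Section 11 withdraws subjects from the treatment period. No arm of the design keeps subjects under observation off drug. Most of this stands: the categories will largely coincide. It does not close the late-stop route in Step 2, or cover a site that completes only the product item.

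Second, SAP 10.1 supplies a label and does not map it to a CRF item. The title of Table 14.3.1.7 is unqualified, and the mock shells are a separate document not available here. The programming may already use the product action. That is fair, and it is why the point says could be left out. The ambiguity is itself a reason to clarify.

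Third, SAP 4.7 cites protocol section numbers and content that do not match the public protocol, so the SAP may have been written against another text. The comparison here is with the public text only.

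A reader might infer several stronger things that the documents do not support:
- **That the protocol commitment is broken or events are lost.** The protocol promises identification, and the full listing of adverse events retains every one.
- **That Table 14.3.1.1 is the only topline view of discontinuation.** Disposition Tables 14.1.2.1 and 14.1.2.2 are also marked topline, and SAP 7.1 has them report the main reason for stopping prematurely. They count premature discontinuations, though, so they might miss a subject who completed Visit 4.
- **That Listing 16.2.7.4 departs from the protocol.** It covers events outside the scope of Protocol 12.6.1.

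**Conclusion.** The mismatch of wording holds, and it is minor. The SAP's discontinuation rows in Table 14.3.1.1, its SOC/PT summary and Listing 16.2.7.2 carry a study-discontinuation label where the public protocol names product discontinuation, and SAP 4.7 is silent. Whether any subject is affected depends on two things the documents do not settle: that the label is programmed literally from the general action, and that at least one TEAE has the product entry without the study entry. The number may be zero. If subjects are affected, each moves the percentage in one arm by about 1.3 points, or the All Doses column by about 0.4. Safety summaries are descriptive and the primary analysis does not depend on this. It is a free improvement in reporting and does not support a claim that tolerability would be materially under-reported.

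**What to change.** In SAP 10.1 (the two overall-table rows and the SOC/PT summary), in Table 14.3.1.7 and in Listing 16.2.7.2, define the category as product action "Investigational product withdrawn" or general action "Discontinued study", and show the two components separately. Table 14.3.1.7 should state the definition in its title or a footnote. Listing 16.2.7.4 may be aligned for consistency. If study discontinuation alone is kept, say so in SAP 4.7.

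The cost is a change of wording and one extra condition on an item that investigators already have to document. It needs no new data, and it is best done before database lock.
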